6.2.2 Adverse Event Monitoring

Adverse events (AEs) and serious adverse events (SAEs) will be recorded from the time a subject signs the ICD until 28 days after the last dose of CC-90009.

Subjects experiencing AEs will be monitored with relevant clinical assessments and laboratory tests, as determined by the Investigator (refer to Section 10 for detailed information). Every attempt will be made to document resolution dates for ongoing AEs. The AEs will be recorded on the AE page of the eCRF and in the subject's source documents.

6.2.3 Vital Signs and Weight

Vital signs include body temperature, blood pressure, pulse rate, and respiration rate and will be recorded at Screening and during the study at various time points for safety monitoring as described in Table 4 – Table 7, Events in Appendix K and Appendices M-O.

In Cycle 1 and for subjects who are administered as in-patient in Cycles ≥ 2 , on days that CC-90009 is administered, vital signs will be obtained prior to dosing (≤ 3 hours), and at 60 minutes (± 15 minutes) and 6 hours (± 1 hr) after the end of the administration of the dose. Starting in Cycle 2 in the outpatient setting, vital signs will be obtained prior to dosing (≤ 3 hours) and at 60 minutes (± 15 minutes) after the end of the administration of the dose. Starting in Cycle 2 in the outpatient setting, vital signs will be obtained prior to dosing (≤ 3 hours) and at 60 minutes (± 15 minutes) after the end of the administration of the dose. Additional vital signs should be

obtained as clinically indicated per the Investigator's medical assessment. Recorded measurements will be captured in the source document and eCRF. The subject's weight will be recorded in the source document and eCRF at the visits listed in Table 4 – Table 7, Events in Appendix K and Appendices M-O.

6.2.4 Physical Examination and ECOG Performance Status

Complete physical examination and ECOG PS (refer to Appendix C) will be performed at the visits listed in Table 4 – Table 7, Appendix K, and Appendices M-O. Results for both will be recorded in the source document. Results for the ECOG PS will also be collected on the eCRF.

Physical examination findings will be classified as either normal or abnormal. If abnormal, a description of the abnormality and clinical importance will be provided in the source documents. Clinically significant changes from baseline will be recorded in the AE section of the eCRF.

6.2.5 12-Lead Electrocardiograms

Triplicate standard 12-lead ECGs will be recorded at the visits listed in Table 4 –Table 7, Appendix K, and Appendices M-O. The 12-lead ECGs (12-lead at 25 mm/sec reporting rhythm, ventricular rate, PR interval, QRS complex, QT interval, and QTc interval) will be performed after the subject has been in the supine position for at least 5 minutes. If the scheduled time for an ECG coincides with a PK blood collection, the blood draw should be performed as scheduled, with the ECG being performed prior to the blood collection.

Triplicate ECGs (3 recordings within 2 ± 1 minute intervals) will be performed at:

- Screening (≥ 72 hours prior to Day 1 with results received from the central ECG laboratory prior to the first dose of CC-90009)
- Cycle 1, Day 1
 - Predose (≤ 60 minutes prior),
 - Post-end of infusion (EOI) at 30 minutes (± 5 minutes), 2 hours, 4 hours, and 8 hours (each ± 30 minutes) [timings are given in reference to the end of the infusion]
- Cycle 1, Day 5 (D1-5 schedule only) or Cycle 1 Day 7 (D1-7 schedule only)
 - If C1D5 or C1D7 is a dosing day, predose (≤ 60 minutes prior) and 30 minutes (± 5 minutes) after the EOI
 - If C1D5 or C1D7 is not a dosing day (eg, D1-3/D8-10 schedule), no ECG done
 - If enrolled on the D1-10 schedule, no ECG done on C1D5 or C1D7
- Cycle 1, Day 8 (C1D8)
 - If C1D8 is a dosing day, predose (≤ 60 minutes prior) and 30 minutes (± 5 minutes) after the EOI
 - If C1D8 is not a dosing day, single time point
- Cycle 1, Day 10 (C1D10)
 - If C1D10 is a dosing day, predose (≤ 60 minutes prior) and 30 minutes (± 5 minutes) after the EOI
 - If C1D10 is not a dosing day (eg, D1-5 or D1-7 schedules), no ECG done

- Cycles ≥ 2 , Day 1
 - predose (≤ 60 minutes prior)

A single ECG will be performed at the EOT visit.

During the Treatment Period, Investigators will make immediate clinical decisions based on their interpretation of the ECG results and provide their overall assessment of the ECG in the eCRF. Clinically significant changes from baseline will be recorded in the AE section of the eCRF.

The ECG outputs will also be uploaded to the central ECG laboratory for definitive analysis and interpretation.

6.2.6 Left Ventricular Ejection Fraction

Left ventricular ejection fraction (LVEF) will be assessed by MUGA scan or ECHO at Screening in all subjects (not required if an assessment has been performed within 28 days prior to the start of study treatment). Follow-up assessments are required as indicated in Table 5, Table 7, Table 32, Table 34, Table 36, or Table 38. Follow-up assessments should use the same procedure used at the screening assessment. A clinically significant reduction is defined as either $a \ge 20\%$ absolute reduction in LVEF or drop to below 45%.

6.2.7 Pregnancy Testing

A FCBP is defined as a female who: 1) has achieved menarche at some point, 2) has not undergone a hysterectomy or bilateral oophorectomy, or 3) has not been naturally postmenopausal (amenorrhea following cancer therapy does not rule out childbearing potential) for at least 24 consecutive months (ie, has had menses at any time in the preceding 24 consecutive months).

The Investigator will classify a female subject as a FCBP according to this definition. Pregnancy testing is not required for non-FCBP subjects but justification must be recorded in the eCRF and the source document. Pregnancy testing will be conducted by the local laboratory.

For a FCBP, pregnancy testing will be conducted at the visits listed in Table 4 – Table 7, Appendix K, or Appendices M-O as outlined in the PPP (refer to Appendix L).

Results for pregnancy tests will be recorded in the source document and eCRF.

6.2.8 Clinical Laboratory Tests

The following laboratory assessments will be performed at the Screening visit and during the study at the time points as described in Table 4 – Table 7, Appendix K, and Appendices M-O. All samples on dosing days should be drawn predose (≤ 5 hours prior) unless otherwise specified. Laboratory assessments will be recorded in the source document and eCRF and are the following:

- Hematology: CBC including hemoglobin, hematocrit, red blood cell count with indices, WBC count with absolute differential (including blast count) and platelet count.
- Serum chemistry: albumin, total protein, bicarbonate or carbon dioxide (CO₂), corrected calcium (corrected for albumin), C-reactive protein (CRP), ferritin, magnesium, phosphorus, creatinine, urea/blood urea nitrogen (BUN), glucose (fasting ≥ 4 hours), potassium, sodium,

chloride, total bilirubin (fractionate if outside normal range), alkaline phosphatase, AST (SGOT), ALT (SGPT), LDH, and uric acid.

- Additional monitoring for TLS (bicarbonate or CO2, phosphorous, creatinine, urea/BUN, potassium, sodium, chloride, LDH, and uric acid) performed in Cycle 1 on Days 1, 2, and 3 at 12 hours (± 1 hour) postdose.
- Additional serum Ca (corrected for albumin) and Mg tests performed in Cycle 1 on dosing days at 6 and 12 hours (± 1 hour) postdose and in Cycles ≥ 2 prior to dosing. For subjects experiencing Grade ≥ 2 hypocalcemia in Cycle 1, additional serum Ca (corrected for albumin) and Mg tests will be performed all dosing days at 6 and 12 hours (± 1 hour) postdose in Cycles ≥ 2. Additional serum PTH tests performed in Cycle 1 on dosing days at 6 hours (± 1 hour) postdose.

NOTE: In the event of Grade ≥ 2 hypocalcemia and abnormal levels of serum albumin, a serum ionized calcium test and more frequent calcium monitoring must be performed (refer to Section 7.2.13.2). Hypocalcemia adverse event grading should be reported as the highest grade determined.

- G6PD at Screening only
- Special calcium metabolism monitoring tests:
 - serum PTH, total P1NP, and serum β -CTx
 - urine calcium/creatinine ratio obtained from spot (random) urine collection
- Serum 25-hydroxyvitamin D level
- Special chemistry: amylase, lipase, T-cell subsets (cluster of differentiation [CD]4+ and CD8+), thyroid-stimulating hormone (TSH; if abnormal reflex to free thyroxine)
- Coagulation: PT, INR, and PTT at Screening and only repeated during the study for subjects on anticoagulation therapy as shown in Table 5, Table 7, Table 32, Table 34, Table 36, or Table 38 and as clinically indicated.
- Urinalysis: dipstick
 - microscopy in the event of a positive (1+ or greater) blood or protein
 - 24-hour collection for creatinine clearance and protein quantification in the event of 2+ or greater protein
- Creatinine clearance determination required at Screening to fulfill inclusion criteria (refer to Section 4.3).

6.2.9 End of Treatment

An EOT evaluation (refer to Table 5, Table 7, Table 32, Table 34, Table 36, or Table 38 for procedures) will be performed for subjects who are withdrawn from treatment for any reason as soon as possible (≤ 28 days) after the decision to permanently discontinue treatment has been made. For subjects who complete dosing in Cycle 4, this visit should be completed on Day 28 (± 2 days) of Cycle 4.

6.3 Follow-up Period

6.3.1 Safety Follow-up

All subjects will be followed for 28 days after the last dose of CC-90009 for AE reporting and concomitant medication information. The 28-day (\pm 3 days) safety follow-up contact may be by telephone. In addition, any SAEs made known to the Investigator at any time thereafter that are suspected of being related to CC-90009 will be reported as described in Section 10.1. Subjects will be followed for all SAEs and all AEs (SAEs and non-serious AEs) associated with confirmed or suspected SARS-CoV-2 infection until resolution, the condition stabilizes, the event is otherwise explained, the event is deemed irreversible, the subject is lost to follow-up, or for suspected cases, until SARS-CoV-2 infection is ruled-out.

Pregnancy testing will be performed per the PPP and Table 5, Table 7, Table 32, Table 34, Table 36, or Table 38.

6.3.2 Efficacy Long Term Follow-up

Subjects without documented progression of disease (or relapse) or start of new anti-cancer therapies will have efficacy evaluations of complete blood counts and peripheral blood smears performed every subsequent 8 weeks (± 1 week) for the 1st year and every 12 weeks (± 2 weeks) for the 2nd year or until progression of disease (or relapse), initiation of a new anticancer therapy, withdrawal from the study, death, or the End of Trial, whichever comes first. A bone marrow evaluation will be completed at the end of the 1st year and as clinically indicated during the Follow-up Period.

Information (including dates) on new anticancer therapies initiated will be collected until progression of disease (or relapse), withdrawal from the study, death, or the End of Trial, whichever comes first.

Information will also be collected on any study drug-related SAEs.

6.3.3 Survival Follow-up

After the Safety Follow-up visit, all subjects will be followed according to the schedule for the efficacy long term follow-up (refer to Section 6.3.2) for survival for up to 2 years or until death, lost to follow-up, or the End of Trial, whichever occurs first. Survival follow-up may be conducted by record review (including public records) and/or telephone contact with the subject, family, or the subject's treating physician.

6.4 Efficacy Assessment

Disease assessments by bone marrow aspiration and biopsy, along with complete blood counts and examination of peripheral blood smears will be performed as indicated in Table 4 – Table 7, Appendix K, or Appendices M-O. In addition, bone marrow aspirates and biopsies must be collected in order to confirm CR or morphologic CR with incomplete blood recovery (CRi) and morphologic CR with partial hematologic recovery (CRh), relapse after CR, CRi, or CRh (as assessed by the Investigator based on CBC with WBC differential results), or disease progression. If disease progression features are observed following the bone marrow evaluation, a repeat bone

marrow evaluation should be performed one month later to confirm disease progression (as described below). Additional aspirates and/or biopsies will be collected as clinically indicated (eg, Cycle 1 Day 15, based on Investigator's medical assessment).

Progressive disease will be defined as:

- A > 50% increase in bone marrow blast count percentage from the baseline (screening) bone marrow blast count that persists for at least 2 bone marrow assessments separated by at least 1 month, unless the baseline bone marrow blast count is > 70%, in which case, a finding of > 70% blasts that persists for 2 post baseline bone marrow assessments separated by at least 1 month would be considered progression, or
- A doubling of the baseline absolute peripheral blood blast count that persists for ≥ 7 days and the final absolute peripheral blood blast count is $> 10 \times 10^9$ /L.

The date of progressive disease is defined as the first date that there was either a > 50% increase in bone marrow blast count from baseline, a persistence of bone marrow blasts > 70% in subject with a baseline bone marrow blast count of > 70%, or a doubling of the peripheral blood blast count.

Treatment failure will be defined as progressive disease or not achieving at least partial remission (PR) by the end of the treatment period. In the absence of progressive disease (as defined above) or unacceptable toxicity, subjects may continue treatment with CC-90009 through Cycle 4 if they are deriving benefit, as judged by the Investigator. Failure to achieve a response and not meeting the criteria for progressive disease will be considered stable disease. Additional cycles of treatment beyond Cycle 4 may be allowed after discussion with the Medical Monitor if the subject is demonstrating clinical benefit (stable disease or PR or CR) and if tolerating the study drug without unacceptable toxicity.

Bone marrow aspirates and biopsies are to be evaluated for morphology, flow cytometry, karyotype, and molecular studies (eg, *FLT3, KIT, NPM1, CEBPa* mutational status if positive on previous bone marrow biopsies). In Part B, bone marrow analyses will be performed at a central laboratory. Molecular and cytogenetic studies may be omitted at the:

- Screening bone marrow evaluation, if they were completed within the prior 90 days and the results are available to enter on the eCRFs,
- Part A, Cycle 1 Day 42 ± 3 days (or at time of hematologic recovery) bone marrow evaluation for subjects with extended safety monitoring in Cycle 1 if a complete response is documented on Day 28.

The marrow aspiration and core sampling (biopsy) should be performed according to the standard of care and analyzed at the local site's laboratory in accordance with the International Council for Standardization in Hematology (ICSH) Guidelines (Lee, 2008).

The clinical activity of CC-90009 will be evaluated by the Investigator by assessing response to treatment according to the IWG Response Criteria in AML (Cheson, 2003; refer to Appendix C).

Treatment decisions will be based on Investigator's assessment. MDS response will be based on the IWG Response Criteria for Myelodysplasia (Cheson, 2006; refer to Appendix G).

Subjects who discontinue treatment for reasons other than disease progression (or relapse), start of a new anticancer therapy, or withdrawal of consent from the entire study will have disease assessments performed up to a maximum of 2 years according to the specified assessment schedule (refer to Section 6.3.2) until progression and/or initiation of new systemic anticancer therapies.

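### AML marrow-progression rule (Section 6.4): baseline blasts of 66.7% to 70% have no attainable marrow criterion, so a marrow-only rise in that band is classed as stable disease

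*Combined protocol and SAP*

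**What the plan says.** Section 6.4 (Efficacy Assessment) gives two routes to progressive disease.

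- **Marrow limb, usual branch:** "A > 50% increase in bone marrow blast count percentage from the baseline (screening) bone marrow blast count", persisting on at least two marrow assessments at least one month apart.
- **Marrow limb, high-baseline branch:** the usual branch applies "unless the baseline bone marrow blast count is > 70" (per cent). Above that value the criterion becomes "a finding of > 70% blasts that persists for 2 post baseline bone marrow assessments", again at least one month apart.
- **Peripheral-blood limb:** "A doubling of the baseline absolute peripheral blood blast count that persists for ≥ 7 days", with a final count above 10 x 10^9/L.

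The date-of-progression sentence in the same section uses the same switch: "a persistence of bone marrow blasts > 70% in subject with a baseline bone marrow blast count of > 70" (per cent). The section also sets the default category: "Failure to achieve a response and not meeting the criteria for progressive disease will be considered stable disease".

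No reason is given for choosing 70% as the switch.

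**The concern.** Replacing the relative-increase criterion at high baselines makes sense only if the replacement begins no later than the point where the increase can no longer be reached. Here it begins later. Between the two points a subject has no marrow route to progression, however far the marrow worsens.

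PFS is a secondary endpoint (Table 3), summarised by Kaplan-Meier medians and rates (Section 9.6.2). A marrow-only progression that cannot be recorded moves the PFS event later or removes it, and the subject is counted as stable. The likely direction is towards longer PFS and more stable disease.

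**Working it through.** **Inputs, all from Section 6.4**

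- Usual branch: follow-up blasts must exceed 1.5 x baseline (a relative increase of more than 50%).
- Switch to the persistence branch: baseline above 70%. A baseline of exactly 70% stays in the usual branch.
- The quantity is a "bone marrow blast count percentage", so its ceiling is 100%.

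**Where the usual branch becomes unattainable**

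1.5 x b >= 100 gives b >= 100/1.5 = 66.67%.

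The plan's switch of 70% is not reproduced by this calculation. The uncovered band runs from 66.67% to 70%, a width of 70 - 66.67 = 3.33 percentage points.

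| Baseline (%) | Branch that applies | Follow-up must exceed (%) | Attainable? |
|---|---|---|---|
| 60 | increase | 90 | yes |
| 65 | increase | 97.5 | yes |
| 66 | increase | 99 | yes |
| 67 | increase | 100.5 | no |
| 68 | increase | 102 | no |
| 69 | increase | 103.5 | no |
| 70 | increase | 105 | no |
| 71 | persistence | 70 | yes |

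Over whole-number baselines from 1 to 100, exactly four can never meet the marrow limb: 67, 68, 69 and 70. The largest possible relative rise is 100/67 - 1 = 49.3% from a baseline of 67%, and 100/70 - 1 = 42.9% from 70%. Both are below the required 50%.

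**Where these subjects end up**

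Table 18 (Appendix C) requires marrow blasts below 5% for the complete-remission and leukemia-free categories, and 5 to 25% for partial remission. A subject whose blasts go from 70% to 100% is therefore not a responder. If the peripheral-blood limb is also unmet, the Section 6.4 default makes that subject stable disease.

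**Does another section close the gap?**

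- Appendix C has no progression category for AML.
- Section 4.2 sets no upper limit on marrow blasts. Its white-cell limit does not cap the marrow percentage.
- Section 9.6 does not redefine progression.

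**Alternative reading**

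If 50% meant percentage points, the limit would be b + 50 >= 100, so b >= 50%. The uncovered band would then be 50 to 70%. The relative reading used here gives the narrower gap.

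**Check of the remedy**

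With the switch at b >= 66.67% and the above-70% finding kept, no whole-number baseline is left without an attainable criterion.

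**The case against.** The strongest reply is that this matters little in practice. The peripheral-blood limb applies at any marrow baseline. The band is just over three points wide. No baseline blast distribution is given, so the number of affected subjects could be zero. MDS has its own progression criteria in Appendix F. All of this stands and limits the size of the point, but it does not supply the missing marrow criterion.

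A second reply is that moving the switch leaves a step: a baseline of 66% would still need more than 99%, while 67% would need more than 70%. That is true. The change makes the criterion attainable at every baseline; it does not make the rule smooth. Within the added band, a finding above 70% is always a rise over a baseline of 70% or less.

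A reader might go further and infer that the above-70% branch is itself an error, because it needs no rise: 71% staying at 71% is progression, and so is 95% falling to 80% and then 71%. The documents do not support calling this an error. Section 6.4 writes a separate branch for these baselines and requires persistence on two post-baseline marrows. Whether persistent blasts above 70% should count as progression is a definitional choice, and the position of the switch does not cause it.

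**Conclusion.** The gap is a matter of arithmetic and holds as stated: a baseline from 66.7% up to and including 70% has no attainable marrow criterion for AML progression. It rests on reading the 50% as a relative increase; the other reading widens the gap.

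The consequence is minor. It touches PFS and the stable-versus-progressive split, which are secondary and descriptive. ORR, CRR and the primary safety and MTD objectives are unaffected. For scale only, one affected subject in a cohort of about 20 with AML is 1/20 = 5% of that cohort.

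Three stronger inferences should not be drawn:

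- **That these subjects can never be called progressive.** The peripheral-blood limb remains open.
- **That final treatment-failure status is wrong.** Section 6.4 counts failure to reach at least partial remission by the end of treatment as treatment failure, so a subject still in this blast range then is a failure either way.
- **That PFS is inflated by a known amount.** Section 9.6.2 does not list PFS events or censoring rules and leaves full efficacy details to the SAP. Without those rules and the baseline distribution, only the likely direction can be stated.

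**What to change.** For the endpoint definition used in PFS and response categorisation only, start the persistence branch where the increase criterion becomes unattainable: baseline blasts of 66.7% or more, that is, 1.5 x baseline >= 100%. With whole-number recording this means 67% or more. Keep the above-70% persistence finding as it is. Make the same change in the date-of-progression sentence, which repeats the 70% switch. State that the 50% increase is relative.

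The Treatment Period text in Section 3.1 and Section 7.2 tie continuation of treatment to progression as defined in Section 6.4. The sponsor should reconcile any effect of the revised wording on those passages. No rule for stopping or continuing treatment is proposed here.

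The cost is a short edit to two places in Section 6.4, carried into the SAP definition. No new data or assessments are needed.

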4.2 Inclusion Criteria

Subjects must satisfy the criteria below to be enrolled in dose escalation (Part A) or dose expansion (Part B) of this study.

- 1) Men and women \geq 18 years of age, at the time of signing the ICD.
- 2) Subject must understand and voluntarily sign an ICD prior to any study-related assessments/procedures being conducted.
- 3) Subject is willing and able to adhere to the study visit schedule and other protocol requirements.
- 4) Relapsed or refractory AML (Parts A and B) or R/R HR-MDS (Part B only) as defined by World Health Organization (WHO) criteria who are not suitable for other established therapies.
 - a) In Part A, R/R AML
 - b) In Part B, R/R AML including
 - Relapsed after allogeneic HSCT or
 - In second or later relapse or
 - Refractory to initial induction or re-induction treatment or
 - Refractory or relapse after HMA treatment (HMA failure defined as primary progression or lack of clinical benefit after a minimum of 6 cycles or unable to tolerate HMA due to toxicity) or
 - Relapsed within 1 year of initial treatment (excluding those with favorable risk based on cytogenetics)
 - c) In Part B, R/R HR-MDS (IPSS-R > 3.5 points, IPSS-R calculated during screening period):
 - IPSS-R intermediate risk (in combination with more than 10% bone marrow blasts or poor or very poor IPSS-R cytogenetic risk) or
 - IPSS-R high or
 - IPSS-R very high risk
- 5) Eastern Cooperative Oncology Group Performance Status (ECOG PS) of 0 to 2.
- 6) At least 4 weeks (from first dose) has elapsed from donor lymphocyte infusion (DLI) without conditioning.
- 7) Subjects must have the following screening laboratory values:

CC-90009-AML-001 Amendment 9 Final: 31 Mar 2022 • Corrected serum Ca or free (ionized) serum Ca within normal limits (WNL).

• Corrected Ca (mg/dL) = Total Ca (mg/dL) – 0.8 (albumin [g/dL] - 4)

- Total White Blood Cell count (WBC) $< 25 \times 10^9/L$ prior to first infusion. Prior or concurrent treatment with hydroxyurea to achieve this level is allowed.
- Potassium and magnesium within normal limits or correctable with supplements.
- Aspartate aminotransferase/serum glutamic oxaloacetic transaminase (AST/SGOT) or alanine aminotransferase/serum glutamate pyruvic transaminase (ALT/SGPT) ≤ 2.5 x Upper Limit of Normal (ULN).
- Uric acid ≤ 7.5 mg/dL (446 µmol/L). Prior and/or concurrent treatment with hypouricemic agents (eg, allopurinol, rasburicase) are allowed.
- Serum bilirubin $\leq 1.5 \text{ x ULN}$.

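### The AML progression date in Section 6.4 is the first date of any > 50% marrow rise or any blood-blast doubling, not the start of the episode that met the progression criteria

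*Combined protocol and SAP*

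**What the plan says.** Protocol Section 6.4 gives three ways to meet progressive disease:

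- Marrow, baseline not above 70%: a rise of more than 50% over the screening value "that persists for at least 2 bone marrow assessments separated by at least 1 month".
- Marrow, baseline above 70%: blasts still above 70% on two post-baseline samples a month or more apart.
- Blood: "A doubling of the baseline absolute peripheral blood blast count that persists for ≥ 7 days", and in addition "the final absolute peripheral blood blast count is" above 10 × 10^9/L.

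The next sentence sets the date. It begins "The date of progressive disease is defined as the first date that there was either a > 50% increase in bone marrow blast count" (relative to baseline), continues with "a persistence of bone marrow blasts > 70% in subject with a baseline bone marrow blast count of > 70"%, and ends "or a doubling of the peripheral blood blast count".

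Table 3 lists PFS among the secondary endpoints. Section 9.6.2 commits to a Kaplan-Meier median PFS with a 95% confidence interval and to rates at selected times. It gives no progression date of its own and leaves full detail to the SAP. The documents contain no other progression date.

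**The concern.** The event and its date are defined by different conditions. A subject needs a confirmed rise to have progressed, but the date attaches to the first rise of any kind. If the qualifying episode is not the first rise, a programmer who follows the sentence assigns a date from an episode that the protocol itself does not regard as progression. PFS would then be too short for that subject, and the progression date could come before a documented response. Two programmers, one literal and one following the presumed intent, could derive different PFS times from the same data.

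**Working it through.** No sample size, power or event count in the documents depends on this rule, so there is no published figure to reproduce. The check sets the two definitions side by side and then applies them to example series.

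**1. Limb by limb (Section 6.4)**

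| Limb | Needed for progression | Needed for the date |
|---|---|---|
| Marrow rise > 50% | two samples, a month or more apart | the rise only |
| Marrow > 70%, baseline > 70% | two samples, a month or more apart | persistence is kept |
| Blood doubling | 7 days or more, final count > 10 × 10^9/L | the doubling only |

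One limb of the date sentence keeps persistence and two do not. None is tied to the episode that qualified.

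**2. Direction.** The dates eligible under the literal rule include the start of the qualifying run, because that start is itself a > 50% rise or a doubling. The earliest eligible date is therefore never later than that start. Any error makes time to progression shorter.

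**3. The blood floor.** With baseline b (in 10^9/L), an exact doubling is 2b. It exceeds 10 only if b > 5. At b = 5, 2b = 10, which is not above 10; at b = 1, 2b = 2. So for any baseline of 5 or less, an exact doubling can set the date without reaching the level that progression requires.

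**4. Two illustrations. The blast values are assumed; neither subject reaches CR, CRi or CRh.**

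*Blood* (10^9/L): baseline 1.0; Day 22, 2.4; Day 28, 1.5; Day 56, 0; Day 140, 6.0; Day 148, 12.0. The doubling threshold is 2 × 1.0 = 2.0.
- Criterion met on Day 148: 148 − 140 = 8 days, final count 12.0 > 10.
- Start of the qualifying run: Day 140.
- Literal date: Day 22, because 2.4 ≥ 2.0.
- Shift: 140 − 22 = 118 days earlier.

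*Marrow* (% blasts): baseline 20; Day 28, 32; Day 56, 4; Day 112, 22; Day 150, 40; Day 182, 45. The threshold is 1.5 × 20 = 30.
- Criterion met on Day 182: two samples above 30, 182 − 150 = 32 days apart.
- Start of the qualifying run: Day 150.
- Literal date: Day 28, because 32 > 30. This precedes the fall below 5% on Day 56 (MLFS if counts have not recovered).
- Shift: 150 − 28 = 122 days earlier.

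**5. Who can be affected.** Section 6.4 treats relapse after CR, CRi or CRh separately, and Appendix C gives relapse after CR its own criterion. Appendix F gives MDS its own progression criteria. That leaves AML subjects with stable disease, PR or MLFS, for whom Appendix C defines no relapse. The group is not empty: in Section 1.2.3.1, 5 of the 13 reported responses are MLFS, and 24 of 82 subjects stopped treatment for progressive disease.

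**6. Plausibility of early rises.** Section 1.3.3 reports that blasts came back between Days 15 and 28 in several patients on Days 1-5 dosing. Section 1.3.4 reports blood-blast increases on non-dosing days of the intermittent schedule. In the open Part B schedule (Table 35), Cycle 1 haematology is drawn on Days 1 to 8, 15 and 22.

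**7. The blood baseline.** Section 6.4 names screening as the baseline for marrow only. Table 35 has two pre-dose blood counts, one at screening and one on Day 1. Section 4.2 says of the white-cell entry limit that "Prior or concurrent treatment with hydroxyurea to achieve this level is allowed", so the two counts may differ.

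**The case against.** The best defence is the ordinary reading. The sentence follows directly on the definition and dates the event just defined, so its limbs can be taken as shorthand for the criteria above. Dating confirmed progression back to its first observation is normal practice and may well be what was meant. That stands as a view of intent. It does not rescue the wording: persistence is repeated in one limb and omitted from two, and no other text supplies the link.

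It is also fair that the SAP could settle the matter, since Section 9.6.2 defers to it, and that no decision depends on this date. Futility uses response (Section 9.3), Part B safety stopping uses toxicity (Section 9.9.3), and ORR and CRR are the efficacy focus (Section 9.6.1).

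A reader might infer more than the documents support:

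- *That an unconfirmed rise counts as progression.* It does not. The full criterion must still be met; only the date is at fault.
- *That a subject in CR, CRi or CRh whose blasts return would be dated before remission.* That return is handled as relapse, and nothing says relapse takes the Section 6.4 progression date.
- *That leukapheresis shortly before dosing distorts the baseline.* Exclusion criterion 10 bars it in the 2 weeks before starting, essentially the window for screening haematology (Day −14 to −1).
- *That frequent sampling guarantees transient doublings.* Section 1.3.3 reports blast reduction persisting through Day 8, and the later rebounds are not said to have doubled the baseline.

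**Conclusion.** Wrong as written, for AML only. The literal date rule can assign progression to an earlier, unrelated and unconfirmed rise, and the resulting error always shortens time to progression. It needs three things in one subject: stable disease, PR or MLFS; an early rise that did not persist; and a separate later progression that did. The shifts of 118 and 122 days show that the error can be material for one subject. They rest on assumed values and are not estimates for this trial, and the documents give no frequency. The effect on PFS also assumes that the AML progression event in PFS takes its date from Section 6.4, the only progression date given. PFS is secondary and descriptive, so this should be corrected but does not threaten the trial's main conclusions.

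**What to change.** Replace the date sentence in Section 6.4 with:

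*The date of progressive disease is the date of the first assessment in the run of consecutive assessments that together satisfy the progression criterion above, including its persistence and, for peripheral blood, the > 10 × 10^9/L requirement; a rise that did not persist does not set the date.*

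State which pre-dose count is the blood-blast baseline, and carry the same wording into the SAP. The cost is one replacement sentence, one baseline statement and the matching derivation. The criteria for progression stay as they are, and no new visits or data are needed.
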